# 2.1. Table 1 - study overview of most recent RCTs evaluating nutritional therapy in medical inpatients

First author year	Patient type	N	Study intervention	Control treatment	Outcomes evaluated	Main effects of study Intervention	Limitations	Ref
Somanchi, 2011	Adult hospitalized medical patients	400	Individualized nutritional counseling	Standard nutritional care	LOS, diagnosis coding of malnutrition cases delays in nutritiona support	Significant reduction in LOS with economic benefit	No patient leve randomization	11
Starke J 2011	Malnourished general medica inpatients	132	Individualized ONS	Standard nutritional care	Caloric intake, weight vitamin levels, QoL complications, readmission, mortality (6m)	Higher caloric/proteir intake, less weight loss increased QoL, fewer complications	time-consuming	12
Rüfenacht U, 2010	Malnourished general medica inpatients	36	Intensive nutritional counseling with ONS	ONS only	Anthropometrics, energy and protein intake, QoL questionnaire	Higher caloric/proteir intake, QoL improvemen after hospitalization	Small sample, two intervention groups	13
Norman K 2008	Malnourished inpatients with GI disease	101	Dietary counseling with ONS over 3- month period		BMI, muscle strength readmission, QoL	Improved hand grip strength and peak flow fewer readmissions, better QoL	two intervention	14
Gariballa SA, 2007	Acutely il inpatients >65y	225	400 ml ONS/d	Standard nutritional care plus placebo	Nutritional status depression (geriatric depression questionnaire), cognitive function	Significant improvement in depression score after 6 month, no difference in cognitive function	High lost to follow number	15
Gariballa S 2006	Malnourished inpatients >65y	445	400 ml ONS/d	400 m placebo/d	Barthel's index readmissions, LOS mortality	Fewer readmissions otherwise no effect	Low adherence or intervention	16
Johansen N, 2004	Malnourished inpatients	212	Individualized nutritional therapy	Standard nutritional care	Caloric intake, LOS complications, mortality QoL	Higher caloric/proteir intake, shorter LOS	Small sample	17
Hickson M 2004	Malnourished medical inpatients, >65 y old	592	0 )	Standard nutritional care	Weight/BMI, Barthel's index, infection, LOS, inhospital mortality	Less antibiotic use otherwise no effect	Short training for health care assistants (15h)	18

BMI, body mass index; d, day(s); GI, gastro-intestinal; h, hours(s); LOS, length-of-stay; m, month(s); ONS, oral nutrition supplement; QoL, quality-of-life

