# 3. Objectives and purpose

# 3.1. Overall hypothesis

Our overall hypothesis states that in acutely-ill medical inpatients at risk for undernutrition, early nutritional therapy to reach nutritional targets is a cost-effective strategy to prevent mortality, morbidity and decline in functional outcomes. The alternative hypothesis is that early nutritional therapy has no beneficial effects, but increases the risk of complications, hospital LOS and overall treatment costs.

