#### Secondary endpoints will be defined as follows:

- (a) each single component of the primary endpoint at day 30
- (b) each single component of the primary endpoint and the combined endpoint at short term, ie, at day 10 or hospital discharge whatever comes first
- (c) each single component of the primary endpoint and the combined endpoint at long term term, ie, at day 180
- (d) short-term nutritional and functional outcomes from inclusion to day 10 or hospital discharge (whatever comes first) including nutritional intake, improvement in muscle strength measured with handgrip strength, lean body mass, changes in undernutrition markers (pre-albumin, retinol-binding protein, body weight, BMI)];

- (e) hospital outcomes measured at hospital discharge defined as total hospital LOS, discharge home vs. post-acute care facility, new decubital ulcer;
- (f) Improvement in quality of life measured on admission and at 30-day and 180-day using the EuroQol Group 5-Dimension Self-Report Questionnaire (Appendix 3) and selected items from the Functional Assessment Anorexia-Cancer Therapy [FAACT] questionnaire),

Safety endpoints including side effects from nutritional therapy will be assessed daily until hospital discharge. A causal relationship with the trial will be rated by two study team members as unrelated / unlikely / possible / probable / definitely / not assessable. The following side effects were defined:

- a) Adverse gastrointestinal effects (diarrhea, nausea, vomiting, abdominal pain)
- b) Complications due to tube feeding or center catheter for parenteral nutrition,
- c) Refeeding syndrome,
- d) Liver or gall bladder dysfunction
- e) Hyperglycemia (defined as glucose levels >12mmol/l or persistent levels >10mmol/l in patients without diabetes or well controlled diabetes)

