# 5. Selection of trial subjects

# 5.1. Recruitment

Upon hospital admission, consecutive adult (age ≥18 years) medical inpatients will be screened for undernutrition risk by the house nursing and /or physician staff, using the well-validated NRS, 2002 edition, as shown in Appendix 2.

Based on this routine screening instrument, we will check daily for eligible patients using the hospital medical information system. Patients can be included in this trial within 24-48 hours of admission if they fulfill the following inclusion criteria

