# 8.2. Statistical approach

Detailed methodology for summaries and statistical analyses of the data collected in this study will be documented in a statistical analysis plan. The statistical analysis plan will be finalized before database closure.

Briefly, a consort diagram will be reported including all screened patients, patients lost to follow up and patients included in the final analyses. Primary and secondary endpoints will be compared between trial arms in the overall ITT population and within predefined subgroups as discussed below. All outcomes will be analyzed in an uncorrected manner as well as jointly corrected for the main risk factors (Barthel's index at baseline, study center and initial NRS categories). For our primary analysis, we will compare the two arms with a chi-square test and we will also estimate effect size with a logistic regression model reporting unadjusted and adjusted odds ratios (OR) and corresponding 95% confidence intervals (CIs).

We will do different predefined subgroup analyses by including interaction terms in the regression models to test for effect modification by important baseline factors. Specifically, we will look at patients age (<60, 60-75, >75 years), gender, risk for undernutrition stratified according to initial NRS (3, 4, >4 points), BMI (<20, 20-25, >25-30, >30), main medical diagnosis (systemic infection, heart failure, acute renal failure, gastro-intestinal disease, tumor), comorbidities (diabetes, chronic renal failure).

For the analysis of functional outcome (defined by Barthel's index) we will use a non-parametric Wilcoxon rank sum test to compare Barthel's index at day 30 between randomization arms. However, to adjust for additional variables, we will also fit a multivariate linear model including Barthel's index at baseline, study center and initial NRS to estimate effect size and 95% confidence intervals (95%Cls). If needed, data will be transformed as appropriate (e.g., log transformation). Moreover, we will assess the progression of Barthel's index over time (i.e. admission, day 8, day 30) using a linear mixed model approach to account for the repeated measurements per patient.

A similar approach will be used for all other secondary endpoints where we will use chi-square tests / logistic regression analysis for binary outcomes, Wilcoxon rank sum test / linear models for continuous outcomes and log-rank test / cox regression for time-to-event data as appropriate.

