# 13.2. Cost-effectiveness analysis of nutritional therapy

**Purpose:** to perform a cost-effectiveness calculation for early nutritional therapy in medical inpatients at risk for undernutrition including cost-effectiveness and cost-utility analyses. These analyses will be from the health-care payers' perspective using intervention data generated in the RCT.

**General approach:** The total cost calculation will include nutritional costs (including nutritional products and estimated time of dieticians spent with patients) and all medical costs within 30 days after study inclusion. The total cost calculation also will include all hospitalisations after index hospitalisation. We

will derive estimates of the real costs using REKOLE a comprehensive accounting algorithm used by Swiss hospitals to internally compute provider costs. Cost-effectiveness will be expressed as the incremental cost-effectiveness ratio. Non-parametric bootstrapping will be used to estimate 95%Cls for differences in incremental costs and effects. We will further calculate the probability value that nutritional therapy is cost-effective for a range of different willingness to pay values. We will define confidence intervals for the relevant cost difference. We will assume equivalence if the difference in total direct costs will lie between the equivalence margins. Non-inferiority of costs will be demonstrated if the upper limit of the confidence interval for cost differences between the two strategies will be smaller than the cost difference. In a second step we will perform a joint analysis of effects and costs in a cost-utility analysis by analysing the cost per quality adjusted life years (QALY) gained. We will present an overall analysis, and different subgroup analyses as defined in the RCT. Specifically, we will look at patients age (<60, 60-75, >75 years), gender, risk for undernutrition stratified according to initial NRS (3, 4, >4 points), main medical diagnosis (systemic infection, heart failure, acute renal failure, gastro-intestinal disease, tumor), comorbidities (diabetes, chronic renal failure), LOS (<8 days, ≥8 days) and BMI (<20, 20-25, >25-30, >30).

**Presentation of results:** To assess the shape of the joint sampling distribution of costs and effects we will present the joint density distribution of incremental costs and effects on the cost-effectiveness plane.

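### Section 13.2 splits the cost-effectiveness results by observed length of stay, a post-randomisation endpoint that is not among the RCT subgroups it says it follows; if the intervention changes length of stay, those stratum results can be misstated.

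*Protocol*

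**What the plan says.** Protocol section 13.2 (cost-effectiveness analysis) announces its subgroups thus: "We will present an overall analysis, and different subgroup analyses as defined in the RCT". It then names seven factors: age, gender, initial NRS, main diagnosis, comorbidities, "LOS (<8 days, ≥8 days" and BMI.

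The RCT subgroups are set out in section 8.2. Interaction terms are to be used "to test for effect modification by important baseline factors", and the list is age, gender, NRS, BMI, main diagnosis and comorbidities. LOS is not on it.

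Section 4.2 places LOS among the secondary endpoints: "hospital outcomes measured at hospital discharge defined as total hospital LOS". Section 5.1 fixes when patients enter: "Patients can be included in this trial within 24-48 hours of admission".

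Two places show that the protocol regards LOS as something nutritional therapy might alter. The alternative hypothesis in section 3.1 is that therapy has no benefit but "increases the risk of complications, hospital LOS and overall treatment costs". Table 1 in section 2.1 records for one earlier trial "Significant reduction in LOS with economic benefit".

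**The concern.** With inclusion one to two days after admission, whether a stay reaches 8 days is settled after allocation. It can therefore depend on the allocation. Suppose the intervention shortens some stays. Patients who would have stayed just over 8 days under control then appear in the <8-day stratum of the intervention arm, while their counterparts in the control arm remain in the ≥8-day stratum. Each stratum then compares different kinds of patients, and randomisation no longer protects the comparison. In-hospital death also ends a stay, so an effect on early mortality could move patients across the cut in the same way.

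The issue is sharper for costs than for most outcomes. Section 13.2 counts all medical costs within 30 days of inclusion, and it bases its cost margin on the cost of one hospital day. Splitting by LOS therefore conditions in part on the quantity being compared. A real saving could look smaller or vanish in both strata, or a difference could appear where there is none.

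Separately from any bias, 13.2 says it takes over the RCT subgroups and then adds one that section 8.2 does not contain. Those two passages need to be reconciled in any case.

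**Working it through.** **Textual check.** Set against section 8.2, the list in 13.2 has exactly one additional item, LOS. It is also the only item on the list that is unknown at randomisation. Where the protocol means a predicted stay it says so: section 5.2 uses an expected LOS of at least 5 days, judged by the treating team. Section 13.2 has no such qualifier, so observed LOS is the natural reading.

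**Numerical illustration.** The plan states no figure on this point to reproduce, and it gives no LOS distribution. All inputs below are assumptions except the 8-day cut.

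- Control stay L is log-normal with median m (7, 8 or 10 days) and log SD s (0.5 or 0.7, with 0.6 for the worked case).
- Intervention stay is max(L − 1, 1), so every stay is one day shorter with a floor of one day.
- Saving means control minus intervention, in days.

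For a log-normal variable with mean M = m·exp(s²/2):

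- E[L | L < c] = M·Φ((ln(c/m) − s²)/s) / Φ(ln(c/m)/s)
- E[L | L ≥ c] = M·[1 − Φ((ln(c/m) − s²)/s)] / [1 − Φ(ln(c/m)/s)]

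An intervention stay is below 8 days exactly when L < 9. Hence the apparent savings are:

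- stratum <8 days: E[L | L < 8] − (E[L | L < 9] − 1), less a small correction for the floor (at most 0.025 day here);
- stratum ≥8 days: E[L | L ≥ 8] − (E[L | L ≥ 9] − 1).

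*Worked case, m = 8, s = 0.6.* M = 8·exp(0.18) = 9.578.

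- Below 8 days, control: 9.578 × 0.2743/0.5 = 5.253. Intervention: 9.578 × 0.3432/0.5778 − 1 = 4.689. Apparent saving 0.564, or 0.558 with the floor.
- At least 8 days, control: 9.578 × 0.7257/0.5 = 13.902. Intervention: 9.578 × 0.6568/0.4222 − 1 = 13.900. Apparent saving 0.002.
- Overall: control 9.578; intervention 0.5778 × 4.695 + 0.4222 × 13.900 = 8.58. Saving about 1.00.

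The day saved has not disappeared. Much of it sits in the change of the <8-day share from 50% to 58%, which a within-stratum comparison discards.

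*Range over the assumptions:*

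| m, s | Share <8 days, control → intervention | Apparent saving, <8 days | Apparent saving, ≥8 days | Overall saving |
|---|---|---|---|---|
| 7, 0.5 | 60.5% → 69.2% | 0.603 | 0.033 | 0.998 |
| 7, 0.7 | 57.6% → 64.0% | 0.597 | −0.105 | 0.984 |
| 8, 0.5 | 50.0% → 59.3% | 0.544 | 0.073 | 0.999 |
| 8, 0.7 | 50.0% → 56.7% | 0.565 | −0.081 | 0.990 |
| 10, 0.5 | 32.8% → 41.7% | 0.456 | 0.169 | 1.000 |
| 10, 0.7 | 37.5% → 44.0% | 0.510 | −0.025 | 0.996 |

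**Other assumed effects**, same six distributions:

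- *No effect on LOS.* The two distributions are identical, so both stratum differences are zero; simulation with 2,000,000 patients per arm gave differences within ±0.01 day.
- *Every stay 10% shorter.* Patients who would stay ≥8 days under control truly save 1.19 to 1.73 days, but the ≥8-day stratum shows 0.41 to 0.92. Those who would stay <8 days truly save 0.47 to 0.59; the <8-day stratum shows 0.14 to 0.22.
- *One day saved only in stays that would be ≥8 days.* The <8-day stratum shows stays 0.27 to 0.33 day longer under treatment, although nobody's stay was lengthened.
- *Every stay one day longer.* The strata show about 0.4 to 0.6 day (<8 days) and about −0.1 to 0.2 day (≥8 days) of extra stay, so added resource use is hidden as well.

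**The case against.** The strongest reply is that the distortion is conditional and the protocol's evidence for an effect on LOS is mixed. Of the four trials in Table 1 that list LOS as an outcome, two report a reduction (n = 400, without patient-level randomisation, and n = 212). The two larger ones (n = 445 and n = 592) report no effect on it. This stands. A reader might infer that the LOS strata are bound to misstate savings; the documents do not support that, because with no effect on LOS the split does no such harm.

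The illustration is also open to challenge. The distribution is assumed. In the worked case it puts about 22% of stays under 5 days (Φ(ln(5/8)/0.6)), although eligibility asks for an expected stay of at least 5 days; expected and actual stays can differ, but the documents do not say by how much. The results are in hospital days. No cost, effect or ratio was simulated, and nowhere does the protocol say that LOS is the main driver of cost. Carrying the result over to costs is a reasonable inference, but it has not been quantified.

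A reader might further infer that wrong treatment decisions would follow. Section 13.2 does speak of informing providers about different types of patients, but it does not name LOS there. Final LOS is also unknown when early therapy starts, so this stratum could hardly be used to select patients. The likely harm is a misleading table.

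What the reply does not remove is that 13.2 prescribes a split on an endpoint the trial itself investigates, under a heading that claims to follow the baseline subgroups of the RCT.

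**Conclusion.** The LOS subgroup in section 13.2 is wrong as written. It conditions on a secondary endpoint measured after randomisation and closely linked to cost, and it contradicts the statement that the subgroups are those of the RCT. The contradiction holds whatever the data show. The bias arises only if the arms differ in LOS, directly or through in-hospital death.

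The size depends on assumptions that the documents cannot confirm. For a uniform one-day saving, both strata understate it in all six distributions examined: roughly half is visible below 8 days and close to none at 8 days or more.

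The scope is narrow: one of seven subgroup factors in an ancillary project. It would be a mistake to read this as a flaw in the overall cost-effectiveness analysis, the six other cost subgroups, the analyses in section 8.2 or the primary endpoint. The overall comparison keeps the full randomised populations and recovers the assumed saving.

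**What to change.** Delete LOS from the subgroup list in section 13.2. The remaining six factors are then those of section 8.2, and the reference to the RCT subgroups becomes true. The cost is one descriptive subgroup table; no data collection or sample size changes. LOS itself stays in the trial as a secondary endpoint compared between the full randomised arms.

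An LOS-type subgroup would be acceptable only if based on a value fixed before randomisation, such as an expected stay in days. The protocol does not say that such a number is recorded. Section 5.2 gives only the threshold of at least 5 days, which every included patient meets, so it cannot form subgroups. Unless a numeric estimate is already captured at inclusion, this option would need a new data item and would not be free.

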# 13.3. Impact of nutritional support on glucose metabolism and insulin regimens

Hyperglycemia and insulin resistance are common in acutely ill medical patients, even in those without a history of diabetes mellitus. We and others found strong associations of hyperglycemia and adverse outcomes of patients with systemic infection hospitalized in the non-critical care setting. Similar data have been found in other patient populations, such as those suffering from stroke. Preclinical data suggest a profound influence of hyperglycemia on immune function. Hyperglycemia interacts in vitro with components of the innate immune system, such as chemotaxis, phagocytosis, and macrophage activation. In animal models of diabetes, hyperglycemia was associated with decreased bacterial clearance and higher infection-related mortality. Generally, hyperglycemia was considered to reflect severity of illness. Yet, provision of nutritional therapy may further increase blood glucose levels and – in the absence of adequate insulin therapy - may thereby contribute to the deleterious effects of hyperglycemia. While the effects of nutritional therapy on glucose metabolism have been well studied in the critical care setting, similar data in medical inpatients are largely lacking.

To close this gap, we will study the influence of nutritional therapy on glucose homeostasis and insulin management as a possible explanation for the higher rates of complication and infection of patients with high caloric intake. Specifically, we will routinely collect information about glucose control, i.e., 4-timesdaily glucose measurements and insulin dose if applicable in all included patients. We hypothesize that hyperglycemia on admission and during inpatient treatment is associated with an adverse disease course, as evidenced by more pronounced inflammatory and stress responses and worse clinical outcomes. To test this hypothesis, we will first investigate the association of initial blood glucose concentrations with clinical outcomes including LOS, disease-specific complications, and mortality. Based on the initial glucose concentration, patients will be priori classified as having normal levels (reference group, blood glucose <7mmol/L), moderate hyperglycemia (blood glucose 7-11mmol/L) or severe hyperglycemia (blood glucose >11mmol/L) based on the classification in a recent publication. In patients with systemic infection, we will used blood levels of CRP and PCT and the white blood cells count at admission and on days 3, 5 and 7 to reflect the inflammatory response. In a second step, we will compare glucose metabolism between randomization arms and investigate whether glucose control with insulin may reduce any harmful effects exerted by hyperglycemia.

This ancillary project will shed light on the important interplay of nutritional therapy and glucose metabolism, and may help to generate preliminary data on the optimal use of insulin in this situation.

# 13.4. Biosampling for later detection of genetic modulators

The term "personalized medicine" relates to the observation that not all patients show the same response to medical therapies. For example, while some patients may show a marked benefit from nutritional therapy, other patients may have no benefit or may even suffer harm from that intervention. Whether or not a patient benefits from nutritional therapy may relate to illness-specific factors (e.g., comorbidities, acute vs. chronic course) or patient-specific factors (e.g., age and gender). Additionally, we hypothesize that genetic signatures exist which will help in identifying patients who may or may not benefit from nutritional therapy.

A number of studies have found an association between specific DNA polymorphisms and the amount, function, or both of the gene products produced in response to pathogenic stimuli. In case of patients with systemic infection and sepsis, for example, these include genes that code for a variety of pattern recognition receptors and polymorphisms have been implicated in mortality. For example, an A to G substitution at the –308 position in the TNF-α promoter was associated with elevated TNF-α expression in vitro and in vivo, and was shown to confer a 4-fold increased mortality in one study of septic shock. The association between gene polymorphisms and medical outcomes awaits large-scale validation. However, there is strong support for the inclusion of genotyping as an important consideration when designing clinical trials such as EFFORT.

To study the impact of genotyping on nutritional therapy, we will perform biosampling in all patients upon their enrolment into this trial (using a separate informed consent). Specifically we will collect one PAXgene Blood RNA tubes (5.0 ml) and one PAXgene Blood DNA tube (8.5 ml) for later mRNA, miRNA and DNA analysis using cutting-edge techniques, such as next generation sequencing (NGS) and microarray analysis in collaboration with Prof. [name] (Department of Endocrinology, University of Fribourg) and the Functional Genomic Center Zurich, with whom we have on ongoing collaboration. This approach proved to be successful as demonstrated by the existence of several "nutrigenomics" networks, aiming to eventually lead to evidence-based nutritional interventions for restoring health and fitness and for preventing diet-dependent diseases (reviewed in). The financial support for this project is not a part of the present proposal.

